## Diarrhea & Abdominal Cramping Management

Diphenoxylate/atropine (Lomotil) 5 mg QID until control (max 20 mg/day); then maintain at 5 mg BID

**Loperamide** (*Imodium/Gastrostop*) 4mg followed by 2 mg Q 4 hours or after each unformed stool (max 16 mg/day); then maintain at 2-4 mg BID

Systemic opioids (e.g. hydromorphone [Dilaudid], codeine) have been found effective in reducing abdominal pain and diarrhea

**Hyoscine butyl** (Buscopan), or hyoscyamine (Levsin) can also be used for abdominal cramps

## 7.1.5 Body Surface Area Calculation

The calculation of the dose of Cetuximab or Panitumumab will be based on the patient's body surface area (BSA). The BSA will be calculated before each cycle, based on the actual height and weight of the patient. The calculated dose will be adjusted downward to the nearest whole milligram.

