# 5.3.2.3 Week 4 (Cycle 1, Day 22)

The following assessments will be made during this visit:

- Karnofsky performance status
- Vital signs (weight, pulse)
- Hematology (see Section 6.3)
- Blood chemistry (see Section 6.3)
- Liver function tests (see Section 6.3)
- Electrolytes (see Section 6.3)
- Urinalysis (see Section 6.3)
- Assess AEs
- Record concomitant medication
- Panitumumab IV infusion, starting at about 3 hours after morning dose of BBI608
- The second dose of BBI608 will be given approximately 12 hours after the first dose.

- Blood samples for pharmacokinetics, (for only the first six patients enrolled in this arm.)
- Dispense BBI608 (two week supply)

Blood samples for pharmacokinetics will be collected immediately prior to the first dose of BBI608 and will continue through 171 hours after administration of the first dose of BBI608. Specific details for the collection of blood samples for pharmacokinetics can be located in Sections 6.4 and Section 16.

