- Intended DI (*dose unit/time unit*) = [intended cumulative dose per cycle] / [intended number of *time units* in a cycle]
- By cycle RDI (%) = $100 \times [by cycle actual DI] / [intended DI]$
- \circ Overall RDI (%) = 100 × [overall actual DI] / [intended DI]

Note the intended dose level is fixed at the start of treatment rather than the start of a cycle

- One exception is for Cetuximab. For Cetuximab, dose level is permitted to change from 400 mg/m^2 on day 5 in cycle 1 to 250 mg/m² for each subsequent infusion. If dose level decreases for Cetuximab 4-7 days after first dose date, then updated dose level is the new intended dose level for Cetuximab.
- Second exception is for all backbone therapies. All backbone therapies incorporate BSA or weight to calculate each dose. Panitumumab incorporates weight to calculate each dose-all other therapies incorporate BSA. Therefore, the BSA to be used for calculating each dose of the backbone therapies will be using the Mosteller method (see below) based on the last available weight and height prior to each infusion. For Panitumumab, the last available weight prior to each infusion will be used for calculating each dose.
- $BSA [m^2] = ((Height [cm] \times Weight [kg])/3600) \times 0.5$
- Calculated doses will be rounded to the nearest integer
- Cumulative dose, actual dose intensity and relative dose intensity will remain missing if they cannot be derived due to missing weight, or BSA. Height from the most recent earlier visit can be used if height is missing.

The intended cumulative dose of napabucasin per cycle is calculated by (intended dose level per day) \times (intended cycle duration in days)

• Intended dose level per day for napabucasin is 500mg po BID

Dose unit of napabucasin is mg, dose unit of other combination drugs (except Panitumumab) is mg/m^2 , dose unit of Panitumumab is mg/kg.

Treatment compliance

Treatment compliance for napabucasin is defined as follows:

(Cumulative actual total dose / total planned or intended dose) $\times 100 = \%$ compliance

For any IV combination drug (Cetuximab and Panitumumab), compliance will be calculated using the following equation:

(Number of treatments administered / number of treatments that should have been administered) $\times 100 = \%$ compliance

For oral combination drug (Capecitabine), compliance will be calculated using the following equation:

(Cumulative actual total dose / total planned or intended dose) \times 100 = % compliance

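### Protocol 7.1.5 bases the panitumumab dose on body surface area, but the drug is dosed at 6 mg/kg, so the rule cannot be carried out for Arm B (minor)

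*Protocol*

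**What the plan says.** Protocol 7.1.5 contains three instructions.

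- Basis: "The calculation of the dose of Cetuximab or Panitumumab will be based on the patient's body surface area (BSA").
- Update: "The BSA will be calculated before each cycle, based on the actual height and weight of the patient".
- Rounding: "The calculated dose will be adjusted downward to the nearest whole milligram".

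Elsewhere the protocol gives panitumumab as 6 mg/kg on days 8 and 22 of each cycle: in the Synopsis under Study Design (Arm B), in the Synopsis under Test Product, and in section 4.1. Section 7.2.2 sets reduced doses only as percentages of the original dose.

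SAP 8.2.1 derives dose intensity on a different footing. It says that panitumumab uses weight and that all other backbone drugs use body surface area (BSA). It specifies "For Panitumumab, the last available weight prior to each infusion will be used for calculating each dose" and adds "dose unit of Panitumumab is mg/kg". For the drugs dosed on BSA it takes the value "based on the last available weight and height prior to each infusion". On rounding it says "Calculated doses will be rounded to the nearest integer".

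**The concern.** Section 7.1.5 is the one place in the protocol devoted to turning a dose level into milligrams for the infused drugs. It names panitumumab explicitly in a complete sentence, so neither text extraction nor redaction explains the conflict. Read with the stated dose, it tells a site to scale a mg/kg drug by square metres. A dosing rule that is wrong for one of three arms should be corrected even if most sites would see through it.

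A smaller matter concerns cetuximab, the drug for which 7.1.5 does work. The rules that sites follow for updating and rounding differ from the rules the SAP uses to calculate the dose. A patient dosed exactly to protocol could then show a relative dose intensity slightly away from 100%.

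**Working it through.** The plan gives no figure to reproduce here. The check is a comparison of texts, with a few illustrative numbers. All body sizes and weight changes below are assumptions, because the documents give none.

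**1. Basis for the panitumumab dose**

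| Place | Basis |
|---|---|
| Protocol Synopsis, Study Design (Arm B) | 6 mg/kg |
| Protocol Synopsis, Test Product | 6 mg/kg |
| Protocol 4.1 | 6 mg/kg |
| Protocol 7.1.5 | BSA, no amount per m² |
| Protocol 7.2.2 | percentage of the original dose |
| SAP 8.2.1 | weight, unit mg/kg |

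The protocol states the dose three times in mg/kg and never in mg/m².

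**2. Can the rule be carried out?**

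A BSA dose is (amount per m²) × BSA, and no amount per m² is given. The only number available is 6, in the wrong unit. Using the Mosteller method named in the SAP, BSA = √(height × weight / 3600):

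| Height, weight | BSA | 6 mg/kg × weight | 6 × BSA |
|---|---|---|---|
| 160 cm, 50 kg | √(8000/3600) = 1.491 m² | 300 mg | 8.9 mg |
| 170 cm, 70 kg | √(11900/3600) = 1.818 m² | 420 mg | 10.9 mg |
| 180 cm, 100 kg | √(18000/3600) = 2.236 m² | 600 mg | 13.4 mg |

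The last column is absurd on its face. The rule does not yield a plausible wrong dose; it yields no usable dose.

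**3. Side note: cetuximab**

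Rounding, at 250 mg/m²:

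| BSA | 250 × BSA | Rounded down (7.1.5) | Nearest integer (SAP) |
|---|---|---|---|
| 1.491 m² | 372.7 mg | 372 mg | 373 mg |
| 1.818 m² | 454.5 mg | 454 mg | 455 mg |
| 2.236 m² | 559.0 mg | 559 mg | 559 mg |

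Rounding down and rounding to nearest can never differ by more than 1 mg.

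Update: weight is scheduled on all four cycle 1 infusion days (5.3.1.2 and 5.3.1.4 to 5.3.1.6), so the per-infusion value can move away from the pre-cycle value. At fixed height the dose ratio is √(new weight / old weight). From 70 kg at 170 cm (454.5 mg):

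- 1 kg: √(71/70) = 1.0071, or 0.7% (3.2 mg)
- 2 kg: √(72/70) = 1.0142, or 1.4% (6.4 mg)
- 5 kg: √(75/70) = 1.0351, or 3.5% (16.0 mg)

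**4. What these differences reach**

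- Compliance for the infused drugs counts infusions, not milligrams (Protocol 7.3, SAP 8.2.1).
- The daily compliance measures in SAP 8.2.1, the term used to define the response evaluable set in SAP 6.3, are for napabucasin.
- Cumulative dose is the sum of doses actually received (SAP 8.2.1).
- What remains is the relative dose intensity of a backbone drug, a descriptive exposure measure that the SAP makes optional.

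**The case against.** The best defence is that no site would be misled. The dose of 6 mg/kg stands in three prominent places. Protocol 7.1.3 sends sites to the product labels for preparation and administration, and the SAP has the right basis. All of this limits the practical effect, and it is why the point is minor. It does not correct 7.1.5, which remains a specific instruction in the governing document. The labels are not reproduced in the text available, so what they say about dose calculation cannot be checked.

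It is also fair to say that an analysis rounding rule need not copy a bedside one. That is why the cetuximab difference is only a side note.

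A reader might infer more from this conflict, in four ways that the documents do not support.

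- *Arm B patients were misdosed.* One could back-calculate a rate, 420 / 1.818 = 231 mg/m², and find 344 mg against 300 mg at 50 kg (+15%) and 517 mg against 600 mg at 100 kg (−14%). No document contains such a rate, so nobody following the protocol could have used it.
- *Weight change within a cycle makes the Arm B dose differ from the SAP dose.* The day 22 visit does record "Vital signs (weight, pulse" and other vital signs. But the per-cycle rule in 7.1.5 governs BSA and sets no update rule for body weight. There is therefore no protocol-defined Arm B dose to compare with the SAP.
- *The two rounding rules often disagree for panitumumab.* How often depends entirely on how finely weight is recorded. At 0.5 kg or 1 kg precision, 6 × weight is always a whole number and they never disagree. The documents state no precision.
- *The primary analysis is affected.* Step 4 of the working shows no route from these rules to the disease control rate.

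**Conclusion.** The point holds, at minor severity. Protocol 7.1.5 is wrong as written for panitumumab and cannot be carried out in Arm B. This rests on the text alone and is certain. The probable consequence is a query to the sponsor. The disease control rate, sample size and decision rules do not change.

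The cetuximab differences in updating and rounding are real but touch only descriptive relative dose intensity. Rounding accounts for at most 1 mg. The update rule accounts for about 0.7% to 3.5% of the dose under the assumed 1 to 5 kg weight changes at 70 kg.

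**What to change.** In Protocol 7.1.5, limit the BSA rule to the drugs dosed in mg/m². That means keeping cetuximab, adding capecitabine (1000 mg/m² in the Synopsis and section 4.1, and BSA-based in the SAP), and removing panitumumab. Then state that panitumumab is dosed at 6 mg/kg of actual body weight. Simply deleting panitumumab would leave capecitabine without any BSA rule. The whole-milligram rounding sentence is best kept to the infusions, since Protocol 7.3 counts capecitabine in capsules.

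The cost is one or two sentences. Optionally, one sentence in SAP 8.2.1 could align the cetuximab update and rounding rules with 7.1.5, or say why they differ.

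Dosing may already be finished: the latest SAP amendment is dated September 2020 and SAP 4.2.2 describes the conduct of the study in the past tense. In that case leave the protocol as it is and note the 7.1.5 error in the clinical study report. The documents do not show that sites followed one common practice, so the report should not assume it.

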## 7.2 Dose Modifications

## 7.2.1 Cetuximab

Infusion Reactions: Reduce the infusion rate by 50% for NCI CTC Grade 1 or 2 and non-serious NCI

CTC Grades 3–4 infusion reactions.

Immediately and permanently discontinue Cetuximab for severe (grade 3 or 4) infusion reactions requiring medical intervention and/or hospitalization.

Dermatological toxicity: If a patient experiences severe acneiform rash (grade 3 or 4), Cetuximab treatment adjustment should be made according to Table 3.

**Table 3. Cetuximab Dose Modification Guidelines for Rash** 

Severe Acneiform Rash	Cetuximab	Outcome	Cetuximab Dose Modification
1st occurrence	Delay infusion 1 to 2	Improvement	Continue at 250 mg/m 
1St Occurrence	weeks	No improvement	Discontinue Cetuximab
2nd occurrence	Delay infusion 1 to 2 weeks	Improvement	Continue at 200 mg/m 
		No improvement	Discontinue Cetuximab
3rd occurrence	Delay infusion 1 to 2 weeks	Improvement	Continue at 150 mg/m 
3rd occurrence		No improvement	Discontinue Cetuximab
4th occurrence	Discontinue Cetuximab		

## 7.2.2 Panitumumab

Infusion Reactions: Reduce the infusion rate by 50% for NCI CTC Grade 1 or 2 and non-serious NCI CTC Grades 3–4 infusion reactions.

Immediately and permanently discontinue Panitumumab for severe (grade 3 or 4) infusion reactions requiring medical intervention and/or hospitalization.

Dermatological toxicity: If a patient experiences dermatological toxicities (grade 3 or 4), Panitumumab treatment should be withheld until the toxicities have improved ( $\leq$  grade 2). Once improved, reinstate Panitumumab administration at 50% of the original dose. If toxicities do not worsen, escalate each additional dose of Panitumumab by 25% increments of the original dose until the recommended starting dose is reached. If toxicity dose not resolve to at least grade 2 after withholding 1 or 2 doses of Panitumumab, or if toxicity worsens or becomes intolerable at 50% of the original dose level, the use of Panitumumab should be permanently discontinued.

## 7.2.3 Capecitabine

## Hematological:

ANC (x10  /L)		Platelets (x10  /L)	1st Event Dose	2nd Event Dose	3rd Event Dose	4th Event Dose
≥ 1.5	and	≥ 75	100%	100%	100%	100%
1-1.49	or	50-74.9	delay* then 100%	delay* then 75%	delay* then 50%	discontinue
0.5 - 099	or	25 - 49.9	delay* then 75%	delay* then 50%	discontinue	discontinue
< 0.5	or	< 25	discontinue or delay* then 50%	discontinue	discontinue	discontinue

\* delay until ANC ≥ 1.5x10^9/L and platelets ≥ 75 x10^9/L

## Hand-Foot Reaction

Grade	1st Event Dose	2nd Event Dose	3rd Event Dose	4th Event Dose
1	100%	100%	100%	100%
2	delay* then 100%	delay* then 75%	delay* then 50%	discontinue
3	delay* then 75%	delay* then 50%	discontinue	discontinue

\* delay until until resolved to grade 0-1

## Other Non-Hematological Toxicity

Grade	1st Event Dose	2nd Event Dose	3rd Event Dose	4th Event Dose
1	100%	100%	100%	100%
2	delay* then 100%	delay* then 75%	delay* then 50%	discontinue
3	delay* then 75%	delay* then 50%	discontinue	discontinue
4	discontinue or delay* then 50%	discontinue	discontinue	discontinue

\* delay until until resolved to grade 0-1

### 7.2.4 BBI608

For any BBI608-related intolerable grade 3 or intolerable grade 2 adverse event, persisting despite optimized medical management, a dose holiday of 1-3 days followed by dose modification is recommended. Dose modification may include reduction of the total daily dose and/or in the number of doses taken per day. Investigators should discuss dose modifications with the medical monitor for the sponsor. Patients may up-titrate dose to full dose as tolerated.

If a toxicity is thought by the Investigator to be related to both BBI608 and the combination drug (Cetuximab, Panitumumab or Capecitabine), then the dose modification rules for both agents should be followed.

## 7.3 Treatment Compliance

A patient is considered compliant with the study protocol when study medication is administered at a compliance level of greater than 80%.

BBI608 compliance will be calculated using the following equation:

(Number of capsules actually ingested /number of capsules that should have been ingested per dose level) x 100= % compliance

Capecitabine compliance will be calculated using the following equation:

(Number of capsules actually ingested /number of capsules that should have been ingested per dose level) x 100=% compliance

Cetuximab or Panitumumab compliance will be calculated using the following equation:

(Number of treatments performed /number of treatments that should have been performed per dose level) x 100=% compliance

## 7.4 Blinding

This is an open label study. Neither the patient nor the investigator and site staff will be blinded to the treatment administered.

## 7.5 Prior Treatment

Reasonable efforts will be made to determine all relevant prior treatments received by the patient within four weeks of the first BBI608 dose. All relevant information must be recorded on the appropriate patient's case report form (CRF). All surgical procedure history, prior chemotherapy and radiation therapy must be recorded on the appropriate CRF.

### 7.6 Concomitant Medication

## 7.6.1 Permitted Treatment

All information regarding concomitant treatments (medications or procedures) must be recorded on the patient's CRF (including the name of the medication or procedure and duration of treatment).

Palliative and supportive care for disease-related symptoms will be offered to all patients in this study. Patients may receive palliative radiation therapy.

BBI608 was shown *in vitro* to inhibit individual CYP P450 isoforms 1A2, 2D6, 2C19, 3A4, and 2C9 with IC50's of 0.25  $\mu$ M, 0.25  $\mu$ M, 2.5  $\mu$ M, 5  $\mu$ M, and 0.5  $\mu$ M respectively. Since *in vitro*, BBI608 has shown the ability to inhibit these CYP P450 isoforms, concomitant use of agents that are substrates of these CYP P450 enzymes should be avoided unless deemed medically necessary by the primary investigator. Examples of commonly prescribed agents that are metabolized by these CYP P450 enzymes are:

NSAIDS: such as ibuprofen, naproxen

Proton pump inhibitors: such as lansoprazole, omeprazole

Oral hypoglycemic medications: sulfonylureas

Beta-blockers: metoprolol, carvedilol

Calcium channel blockers: amlodipine, diltiazem, nefedipine, verapamil

Antidepressants: paroxetine, imipramine, amitriptyline Anti-epileptics: such as phenytoin, phenobarbitone Anti-

psychotics: such as haloperidol, risperidone Antibiotics: such as clarithromycin, erythromycin

HMG CoA reductase inhibitor: atorvastatin, lovastatin, simvastatin

Anesthetics: such as halothane, enflurane;

HIV antivirals: such as saquinavir, indinavir, ritonavir

Immunomodulators (immunosuppressives): such as cyclosporine, tacrolimus

Steroids: such as hydrocortisone, estrodiol

BBI608 is metabolized by the CYP P450 isoform 1A2. Therefore, concomitant use of drugs which inhibit CYP1A2 should be avoided unless deemed medically necessary by the primary investigator. Known drugs that inhibit CYP 1A2 include ciprofloxacin and other fluoroquinolones, Fluvoxamine Verapamil, amiodarone, interferon, methoxsalen, enoxacin, mexiletine, and ticlopidine

In addition, the following treatments are allowed:

- Standard therapies for concurrent medical conditions
- Epoetin alfa (Epogen®, Procrit®)
- Hematopoietic growth factors, including filgrastim (Neupogen®), or other granulocyte colony stimulating factors (G-CSF), are permitted following documented and clinically significant neutropenia after the patient has completed at least one cycle of treatment with BBI608
- Prophylactic antiemetics may be administered according to standard practice
- Megestrol acetate (Megace®)
- Dethamethasone
- Diphenhydramine
- Cimetidine
- Ranitidine

## 7.6.2 Prohibited Treatment

- Any other concurrent chemotherapy, non-palliative radiotherapy, hormonal therapy, or immunotherapy
- Other investigational agents
- Immunosuppressive therapies, including systemic corticosteroids (except when used intermittently in an antiemetic regimen or when prescribed at a non-immunosuppressive dose for treatment of fatigue and low-appetite)

### 8 SAFETY ASSESSMENTS

### 8.1 Adverse Events

## 8.1.1 Assessments

The Investigator is responsible for monitoring the safety of patients who have enrolled in the study. All AEs considered to be related to BBI608 occurring after any administration of the study drug will be followed until the event resolves. AEs will be evaluated using the National Cancer Institute (NCI) CTCAE, Version 4.0, published 28 May 2009.

Investigators are required to document all AEs occurring during the clinical trial, commencing with the first dose of BBI608 and including the protocol-defined post-treatment follow-up period (21 Code of Federal Regulations [CFR] §312.64[b]) on designated CRF pages. AEs occurring following the signature of the informed consent, but prior to the first dose of study drug will not be reported as AEs. It is also important to record all AEs that result in permanent discontinuation of the investigational product being studied, whether serious or non-serious.

Serious adverse events (SAEs), as defined below, must be reported to Boston Biomedical Inc. or its representative within 24 hours of knowledge of their occurrence.

## 8.1.2 Definitions

An AE is defined as any untoward medical occurrence in a patient or clinical investigational patient administered a pharmaceutical product that does not necessarily have to have a causal relationship with the treatment. An AE can therefore be any unfavorable and unintended sign (including an abnormal laboratory finding, for example), symptom, or disease temporally associated with the use of a medicinal product, whether or not considered related to the medicinal product.

Laboratory data are to be collected as stipulated in this protocol, and toxicity trends will be analyzed utilizing objective toxicity criteria. Clinical syndromes associated with laboratory abnormalities are to be recorded as appropriate (e.g., diabetes mellitus instead of hyperglycemia).

Progression of disease is considered an efficacy outcome parameter and should not be captured as an AE. A non-serious AE is any untoward medical occurrence that does not meet any of the criteria for SAEs as defined below.

Patients should be instructed to report any AE that they experience to the investigator. Investigators should assess the patient for AEs at each visit. AEs occurring during the clinical trial and the follow-up period should be recorded on the appropriate AE CRF. To capture the most potentially relevant safety information during a clinical trial, it is important that investigators record accurate AE terms on CRFs.

Wherever possible, a specific disease or syndrome rather than individual associated signs and symptoms should be identified by the investigator and recorded on the CRF. However, if an observed or reported sign or symptom is not considered a component of a specific disease or syndrome by the investigator, it should be recorded as a separate AE on the CRF.

### **8.2** Serious Adverse Events

### 8.2.1 Definitions

A serious adverse event (SAE) is any adverse experience occurring at any dose that results in any of the following outcomes:

[figure not shown]
- Death
- A life-threatening adverse drug experience
- Inpatient hospitalization or prolongation of existing hospitalization, except for events that are clearly disease related
- A persistent or significant disability/incapacity
- A congenital anomaly/birth defect

Important medical events may be considered an SAE based upon appropriate medical judgment.

Under this protocol, scheduled hospitalizations or elective surgical procedures will not be considered SAEs. Prolongation of a scheduled hospitalization can be considered an SAE. Complications associated with scheduled procedures are considered an AE.

